8.5.2. Other Clinical Laboratory Tests

At screening, patients will be tested for HBcAb and HBsAg, antibodies to hepatitis C virus (reflex viral RNA testing if hepatitis C antibodies present), human immunodeficiency virus types 1 or 2, and enteric pathogens (including stool culture and *Clostridium difficile* toxin assay; additional testing [eg, ova and parasites] may be performed at the investigator's clinical discretion).

If HBcAb is positive and HBsAg negative, hepatitis B viral DNA will be done as reflective test, and, if undetectable, then not exclusionary.

Patients will also be tested for TB at screening (QuantiFERON[®] TB Gold Test). Patients with confirmed positive results will not be eligible to participate in the study (unless documentation of prior TB treatment is available).

If the QuantiFERON[®] TB Gold Test is negative at screening, then the patient may proceed in the screening period. However, if the QuantiFERON[®] TB Gold Test is deemed by the principal investigator to be a false positive at screening, then a second sample should be drawn and the following steps taken:

- If the second QuantiFERON[®] TB Gold Test is positive (ie, results match the first test), then the patient will be a screen failure.
- If the second QuantiFERON[®] TB Gold Test is negative (ie, results do not match the first test), then a third sample should be drawn.
 - If the third QuantiFERON[®] TB Gold Test is positive (ie, results match the first test), then the patient will be a screen failure.
 - If the third QuantiFERON[®] TB Gold Test is negative (ie, results match the second test), then the patient may proceed in the screening period.

In case of a suspected liver injury, additional laboratory tests will be required (see [Appendix K](#)).

8.5.2.1.Human Chorionic Gonadotropin Tests

HCG tests in serum and in urine will be performed for women of childbearing potential at the time points detailed in [Table 1](#).

8.5.2.2.Follicle-Stimulating Hormone

At screening, women who have been amenorrheic for at least 1 year without an alternative medical cause will have a serum FSH assessment to confirm postmenopausal status (an increased concentration of FSH of more than 35 IU/L in women not using hormonal contraception or hormonal replacement therapy).

8.6. Physical Examinations

Physical examinations will be performed at the time points detailed in [Table 1](#). Any physical examination finding that is judged by the investigator as clinically significant (except at the initial screening visit, which will be captured as medical history) may be considered an adverse event, recorded on the CRF, and monitored as described in Section [8.1.3](#). Physical exam findings that are attributable to another adverse event would not be reported as separate adverse events.

A full physical examination will include at a minimum the following organ systems:

- General appearance
- Head, eyes, ears, nose, mouth, and throat
- Chest and lungs
- Heart
- Abdomen
- Musculoskeletal
- Skin
- Extremities
- Lymph nodes
- Neurological

Height and weight will be obtained at the at the time points detailed in [Table 1](#).

A brief physical examination will include at a minimum general appearance; head, eyes, ears, nose, mouth, and throat; chest and lung; heart and extremities (including pulses).

8.7. Vital Signs

Vital signs (blood pressure [systolic/diastolic], respiratory rate, body temperature, and pulse rate) will be measured at the time points detailed in [Table 1](#). Patients are to remain in a supine position for at least 5 minutes prior to measuring blood pressure and pulse rate. If possible, blood pressure measurements should be completed on the same arm at each visit. All vital signs results outside of the reference ranges will be judged by the investigator as belonging to 1 of the following categories:

- abnormal and not clinically significant
- abnormal and clinically significant

For any abnormal vital sign value, the measurement should be repeated as soon as possible. Any vital sign value that is judged by the investigator as clinically significant will be recorded both on the source documentation and the CRF as an adverse event and monitored as described in Section 8.1.3.

8.8. **Electrocardiography**

A 12-lead ECG will be recorded at the time points detailed in [Table 1](#). ECGs should be performed in a supine position after 5 minutes rest.

ECG review and assessment will be done both by the investigators and by a centralized ECG reading vendor.

All ECG results outside of the reference ranges will be judged by the investigator as belonging to 1 of the following categories:

- abnormal and not clinically significant
- abnormal and clinically significant

Any ECG finding that is judged by the investigator as clinically significant (except at the screening visit[s]) will be considered an adverse event, recorded on the source documentation and in the CRF, and monitored as described in Section 8.1.3.

Where triplicate measurements are required (at screening), each ECG will be taken within 1 to 5 minutes of the previous one.

9. ASSESSMENT OF PHARMACOKINETICS/ PHARMACODYNAMICS/BIOMARKERS/ PHARMACOGENETICS/IMMUNOGENICITY

9.1. Pharmacokinetic Assessment

Blood samples will be collected via venipuncture at the time points detailed in [Table 1](#) for measurements of serum concentration of TEV-48574. At visits where IMP is administered, samples should be taken prior to IMP administration (ie, trough levels).

Additionally, efforts should be made to determine serum concentration of TEV-48574 in cases of suspected severe, systemic hypersensitivity reaction, or anaphylaxis; serious adverse event; or immunogenicity-related adverse events.

The dates and times of IMP administration and the date and time point (24-hour clock time) of each pharmacokinetic sample will be recorded both on the source documentation and the CRF.

Samples will be analyzed for concentration of TEV-48574 using an appropriate validated method. Incurred sample reanalysis may be performed. Blood samples from patients who received placebo will not be analyzed.

Blood volumes are provided in the ICF and Laboratory Manual. Details on sample handling, storage, shipment, and analysis are provided in the Laboratory Manual.

9.2. Pharmacodynamics Assessment

All PD potential parameters tested in this study are exploratory markers and are described in Section [9.4](#).

9.3. Immunogenicity Testing

Blood samples for ADA testing will be collected via venipuncture at the time points detailed in [Table 1](#). Details on sample handling, storage, shipment, and analysis are provided in the Laboratory Manual.

Additionally, efforts should be made to collect ADA samples in cases of suspected severe, systemic hypersensitivity reaction, or anaphylaxis; serious adverse event; or immunogenicity-related adverse events. In cases of suspected or confirmed anaphylaxis, efforts should be made to collect samples as close to the onset of the event as possible, at resolution, and 30 days after onset of the event. Antibodies to TEV-48574 will be evaluated in serum samples.

All samples collected for detection of antibodies to TEV-48574 may also be evaluated for TEV-48574 serum concentration to facilitate interpretation of the antibody data. Confirmed ADA positive samples may be further evaluated for TEV-48574 neutralizing antibodies.

The dates and times of IMP administration and the date and time point of each immunogenicity sample will be recorded both on the source documentation and the CRF.

The detection and characterization of antibodies to TEV-48574 will be performed using validated assay methods. Blood samples from patients who received placebo will not be analyzed by the ADA assay.

A patient will be classified as having a treatment-emergent ADA response if either: 1) the patient had a positive sample at any of the time points after first dose of IMP but not at the time point before first dose of IMP, or 2) the patient had positive samples before first dose of IMP and 1 or more time points after first dose of IMP, with at least a 4-fold increase in titers after first dose relative to the sample ADA titers before first dose. Where possible, the impact of the presence of ADAs on pharmacokinetics and clinical safety will be evaluated.

Samples may be stored if permitted by the ICF and local regulations after the last patient's last visit for the study at a facility selected by the sponsor to enable further analysis of immune responses to TEV-48574.

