^j Serology includes hepatitis B core antibody and surface antigen, hepatitis C virus, and human immunodeficiency virus types 1 or 2. Patients with HBcAb positive and HBsAg negative serology and undetectable Hepatitis B viral DNA at screening may have follow-up Hepatitis B viral DNA testing throughout their participation in the study.

^k If the QuantiFERON® TB Gold Test is deemed by the principal investigator to be a false positive, additional sample will be tested to confirm the diagnosis.

^l Clinical laboratory tests including serum chemistry and complete blood count (hematology). Patients should be fasting for at least 8 hours prior to safety laboratory assessments only at the screening, week 14, and early termination visits (ie, visits at which low density lipoprotein, high density lipoprotein, and triglycerides will be measured). Coagulation tests (PT/PTT/INR) will be performed at screening only or in case of suspected liver injury (see [Appendix K](#)). The hematocrit value measured at screening will be used to calculate the baseline CDAI score. Screening laboratory test abnormalities, if considered by the Investigator to be transient and inconsistent with the patient's clinical condition, may be repeated once during the screening period for confirmation.

^m When sampling urine, menstruation status should be recorded for women of childbearing potential.

ⁿ If sample has not been collected at this visit, it could also be collected at one of the following visits.

^o In cases of a suspected severe systemic hypersensitivity reaction (eg, anaphylaxis), serious adverse event, or immunogenicity-related adverse event, efforts should be made to collect additional sample(s) for immunogenicity, serum total and free TL1A, and serum concentration of TEV-48574. In cases of suspected or confirmed anaphylaxis, efforts should be made to collect samples for ADA determination as close to the onset of the event as possible, at resolution, and 30 days after onset of the event. Confirmed ADA positive samples may be further evaluated for TEV-48574 neutralizing antibodies.

^p Proteomics and potentially autoantibodies (pANCA, ASCA).

^q At visits where IMP is administered, samples should be taken prior to IMP administration (ie, trough levels).

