
A secondary objective of the study is to evaluate the safety and tolerability of 2 different doses of TEV-48574 sc administered Q2W in adult patients with IBD (moderate to severe UC or CD).
	
The safety and tolerability measures/parameters are as follows:
 
 • Adverse events • Change from baseline in clinical laboratory test results (serum chemistry, hematology, and urinalysis) • Change from baseline in vital signs measurements (blood pressure, pulse rate, body temperature, and respiratory rate) • Change from baseline in 12-lead electrocardiogram findings • Patients who stopped the investigational medicinal product due to adverse events • Local tolerability at the injection site

A secondary objective of the study is to evaluate the immunogenicity of 2 different doses of TEV-48574 sc administered Q2W in adult patients with IBD (moderate to severe UC or CD).
	
The immunogenicity endpoints for this study are as follows:
 
 • Change from baseline in treatment-emergent anti-drug antibody (ADA) at weeks 2, 4, 8, 14, and follow-up visit • Presence of neutralizing ADA in ADA positive patients at weeks 2, 4, 8, 14, and follow-up visit

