10.2.6. Immunogenicity Analysis Set

The immunogenicity analysis set will include all patients in the safety set who receive TEV-48574 and who have at least 1 reportable immunogenicity result.

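### The immunogenicity rules do not deliver the stated secondary endpoints: neutralizing testing is optional, pre-dose-only patients enter the analysis set, and ADA status can depend on event-triggered samples

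*Protocol*

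**What the plan says.** **Endpoints.** Section 3.1 lists two secondary immunogenicity endpoints: "Change from baseline in treatment-emergent anti-drug antibody (ADA) at weeks 2, 4, 8, 14, and follow-up visit", and whether neutralizing ADA is present in ADA-positive patients at the same five time points. Table 1 and Appendix A schedule ADA and neutralizing ADA together at these visits, at day 1 and at early termination.

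**Neutralizing assay.** Section 9.3 says "Confirmed ADA positive samples may be further evaluated for TEV-48574 neutralizing antibodies". Table 1 footnote o repeats this, and Section 10.12 leaves further characterization of confirmed positives to be done as needed.

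**Analysis set.** Section 10.2.6 takes safety-set patients "who receive TEV-48574 and who have at least 1 reportable immunogenicity result". It does not ask for a post-dose result.

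**ADA status.** Under the first limb of the Section 9.3 definition, a patient is treatment-emergent positive if "the patient had a positive sample at any of the time points after first dose of IMP" and the pre-dose sample was not positive. The second limb needs a 4-fold titer rise after dosing.

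**Extra samples.** Section 9.3 adds that "efforts should be made to collect ADA samples in cases of suspected severe, systemic hypersensitivity reaction, or anaphylaxis; serious adverse event", or for immunogenicity-related events. For anaphylaxis, suspected or confirmed, the request names three times: "efforts should be made to collect samples as close to the onset of the event as possible, at resolution, and 30 days after onset". Footnote o attaches the same instruction to the ADA row of Table 1: "efforts should be made to collect additional sample(s) for immunogenicity, serum total and free TL1A, and serum concentration of TEV-48574".

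**Use of the status.** Section 9.3 states that, where possible, "the impact of the presence of ADAs on pharmacokinetics and clinical safety will be evaluated". Section 10.12 only says that this may be assessed, and refers back to Section 9.3 for the definition.

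**The concern.** The endpoints, the assay rules, the analysis set and the status definition do not fit together.

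- **(a)** An endpoint listed without qualification depends on a test that nobody is obliged to run. If only some confirmed positives are tested, the proportion neutralizing has a numerator and denominator that depend on an unstated choice.
- **(b)** Both limbs of the treatment-emergent definition need a post-dose sample. A patient with only a pre-dose result cannot meet either, but counts in the denominator as a non-event.
- **(c)** Extra ADA samples are drawn because an adverse event occurred. If they count toward patient-level status, the outcome influences how often the exposure is looked for, and the same status then serves the comparison of ADA with safety.

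At stake are the immunogenicity results of this trial, a stated secondary objective. No primary efficacy analysis is touched.

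**Working it through.** There is no design figure to reproduce here. The two earlier ADA rates in Section 2.2.2.1.3 check: 23/48 = 47.9% and 3/27 = 11.1%.

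**(a) Neutralizing ADA.** Side by side: Section 3.1 names the endpoint at five time points; Table 1 schedules it; Sections 9.3 and 10.12 and footnote o make the assay discretionary without a criterion. No number is needed to see the conflict.

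**(b) Denominator.** With true incidence *p* among patients with a post-dose result, and a share *s* of the set having only a pre-dose result, reported incidence is *p*(1 − *s*). For *p* = 10% and *s* = 5% (both assumed): 0.10 × 0.95 = 9.5%.

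**(c) Unequal sampling.** Inputs from the protocol: 5 scheduled post-dose samples (weeks 2, 4, 8, 14, follow-up); 3 triggered samples for anaphylaxis; about 160 active patients (2 arms × 80). Assumed: no true link between ADA and the event; independent, transient positivity per sample; one extra sample for triggers other than anaphylaxis, where no number is given.

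For any-of-5 incidence *p*₀, the per-sample probability is *q* = 1 − (1 − *p*₀)^(1/5). With *k* extra samples, *p*₁ = 1 − (1 − *q*)^(5+*k*), and OR = [*p*₁/(1 − *p*₁)] / [*p*₀/(1 − *p*₀)].

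Example at *p*₀ = 11.1%: *q* = 0.0233; one extra sample gives *p*₁ = 13.2% and OR = (0.1317/0.8683)/(0.111/0.889) = 1.22; three give 17.2% and OR 1.66.

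| Any-of-5 incidence | 1 extra: ADA+ (OR) | 3 extra: ADA+ (OR) |
|---|---|---|
| 5% | 6.0% (1.21) | 7.9% (1.63) |
| 11.1% | 13.2% (1.22) | 17.2% (1.66) |
| 47.9% | 54.3% (1.29) | 64.8% (2.00) |

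Two sensitivity cases over the same three incidences:

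- *Half of positives persistent*, so that extra samples add nothing for them: OR 1.10 to 1.16 with one extra sample, 1.31 to 1.53 with three.
- *Event patients keep only 3 scheduled samples* because treatment stops: OR 0.75 to 0.80 with one extra, 1.00 with two, 1.21 to 1.29 with three.

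As a gauge only, since the protocol plans no such test: a one-sided 5% Fisher test in 160 patients, with event rates of 5% or 10% (assumed) and 2,000 simulations per setting, rejects in 1.5% to 3.0% of trials with no extra samples, 2.6% to 6.9% with one, and 5.0% to 26.0% with three. The top value needs 47.9% incidence and three extra samples in every event patient.

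**Incidence to expect.** At 400 mg and above, Sections 2.2.2.1 and 2.2.2.1.3 imply 12 single-dose subjects (2 cohorts × 6) and 18 repeat-dose patients (2 cohorts × 9) on active drug, with 1 positive: 1/30 = 3.3%. Put into the formula, this gives 4.0% with one extra sample and 5.3% with three.

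**The case against.** A reader might infer that the ADA-safety evaluation is biased toward an association. The documents do not support that.

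- **Reading.** Section 9.3 opens with ADA sampling at the Table 1 time points and introduces triggered samples separately, so the definition's time points may mean the scheduled ones. Against that, the same section records a time point for each immunogenicity sample, and footnote o ties triggered samples to the Table 1 row. The text is ambiguous, which is all that is claimed.
- **No fixed analysis.** The look at safety is conditional in Section 9.3 and optional in Section 10.12, with no test or decision attached. This stands and limits the stakes.
- **Direction.** Under Section 4.4.1.1, severe hypersensitivity reactions and serious events judged possibly related stop treatment. Later scheduled samples may then be lost, and the distortion can vanish or reverse. This stands. Withdrawn patients do have an early-termination ADA sample and are encouraged to complete follow-up, while extension entrants skip the follow-up sample, so sampling stays unequal either way.
- **Size.** Inflation of roughly 1.5-fold in the positive rate needs three extra samples and mostly transient, independent positivity. Three are requested only for anaphylaxis, and the day-30 sample can nearly coincide with a scheduled one: a day 1 reaction gives day 31, against the day 29 visit.
- **Removing triggered samples** from every comparison would class as negative a patient whose only positive was drawn at the reaction. That objection is sound and shapes the fix.

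On (a), Table 1 does schedule neutralizing ADA, and Section 6.9.2 keeps clinical data from bioanalysis staff, which limits selection on outcome. Neither obliges anyone to run the assay. On (b), the effect is small. The change-from-baseline wording of the other endpoint is loose, but Section 9.3 defines the status relative to the pre-dose sample, so rewording it is editorial.

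**Conclusion.** The point holds in three parts of unequal weight.

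- **(a)** This is the main defect and rests on the text alone: a secondary endpoint at five time points depends on an optional assay.
- **(b)** This also follows from the text. Its effect is slight: 10% reported as 9.5% if 5% of the set have no post-dose result, a share the protocol does not give.
- **(c)** This is conditional. As literally worded, the definition can take in event-triggered samples and so distort a comparison of ADA with safety. With one extra sample the null odds ratio is about 1.1 to 1.3. With three it is about 1.3 to 2.0, depending on incidence and persistence. If scheduled samples are lost after the event, it runs from 0.75 to 1.29. Incidence, persistence, event rates and extra-sample numbers outside anaphylaxis are assumptions. A definite bias in one direction is not established.

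**What to change.** 1. **Sections 9.3 and 10.12, and Table 1 footnote o:** state that all confirmed ADA-positive samples *will be* tested for neutralizing antibodies, and drop the as-needed condition. At 3.3% incidence this concerns about 160 × 0.033 ≈ 5 active patients; at 11.1%, about 18.
2. **Section 10.2.6:** require at least 1 reportable post-dose immunogenicity result. This adds one condition to the set.
3. **Section 9.3:** keep patient-level status based on all samples, and say so expressly. For any comparison of ADA with safety, add a sensitivity version based on scheduled samples, counting the early-termination sample as scheduled. List triggered samples with their timing relative to event onset. This costs one derived flag and one listing.

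Sample collection stays as it is. Event-triggered results remain fully visible, and a positive found only at a reaction still counts in the main status.

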9.4. Assessment of Exploratory Biomarkers

Potential exploratory biomarker objectives include characterization of TEV-48574 responders, identification of tissue-, fecal-, and blood-based-resident proteomic or transcriptomic biomarkers indicative of TEV-48574 mechanism of action and PD, development of scalable tools to identify likely responders in future studies, and elucidation of TL1A-mediated pathway(s) that drive IBD in responders within the target patient population.

The following exploratory biomarker assessments will be pursued from samples collected at indicated time points ([Table 1](#)):

- Serum free and total TL1A levels will be measured using qualified/validated assay methods. Tissue TL1A protein expression will also be assessed.
- Serum proteomic markers assertive of PD and mechanism of action effects will be pursued by singleplex or multiplex assays. [REDACTED] will be collected and may be analyzed for evaluation of target engagement, PD, and mechanism of action.
- Serum level of autoantibodies involved in IBD, such as perinuclear antineutrophil cytoplasmic antibodies (pANCA) or anti-*Saccharomyces cerevisiae* antibodies (ASCA), could also be measured to test the correlation with the response to TEV-48574
- Serum and tissue markers of GI tissue condition (eg, fibrosis/remodeling) will be assessed by transcriptomic and/or specific proteomic assays.
- GI transcriptome will be assessed from biopsies by RNASeq to characterize TEV-48574-mediated responses or TEV-48574-responsive patients.
- Fecal calprotectin or other stool-derived markers as a tissue proximal marker of GI inflammation
- High sensitivity C-reactive protein (hsCRP) as a peripheral marker of inflammation
- UC-100 score ($1+16 \times$ Mayo stool frequency subscore [0 to 3] $+6 \times$ Mayo endoscopic subscore [0 to 3] $+1 \times$ RHI score [0 to 33]); ranges from 1 (no disease activity) to 100 (severe disease activity) ([Jairath et al 2019](#))

Details of the specimen collection, processing, and handling requirements are provided in the Laboratory Manual.

Residual biopsy, fecal, and blood samples, after appropriate analysis to support this study, may be stored at a Teva-secured facility for up to 15 years towards future analysis related to TEV-48574 or IBD if permitted by the ICF and local regulations.

Exploratory biomarker analyses may be presented in a separate analytical plan and report at the end of the study.

